2.7 DATA ANALYSIS

For both primary safety endpoints 1 and 2, pooling of data from the Corox OTW BP, Corox OTW-S BP, and Corox OTW-L BP LV leads will be justified as part of the final data analysis. The differences in outcomes for the Corox OTW BP, Corox OTW-S BP, and Corox OTW-L BP LV leads will be tested using an exact, Chi-square test. If no evidence is found of differences between the Corox OTW BP, Corox OTW-S BP, and Corox OTW-L BP LV leads ($p > 0.05$), then the results will be considered poolable for purposes of testing the protocol hypotheses associated with the two primary endpoints. If evidence of differences is found for a given endpoint, then the hypotheses for that endpoint will additionally be tested separately for each LV lead.

CELESTIAL REGISTRY PROTOCOL

Primary safety endpoint 1 will be evaluated by performing an exact, noninferiority test comparing a binomial proportion (overall SAE free-rate at 5 years) to 92.5%, with a noninferiority delta of 5%. Equivalently, the upper, one-sided 95% confidence bound for the absolute difference between the overall SAE free-rate and 92.5% must not exceed 5%.

The evaluation of primary safety endpoint 2 will be based on the exact, two-sided 95% confidence interval for the observed, individual SAE rates at 5 years. The upper bound of these 95% confidence intervals must be less than 1%.

The secondary endpoint of successful biventricular pacing will be summarized as a success rate at each of the scheduled CELESTIAL follow-up visits through 5 years post-enrollment, together with the associated exact, 95% confidence intervals.

The secondary endpoint of other SAEs at 5 years, which were excluded from the primary safety analyses (listed in Table 5), will also be summarized as SAE rates together with their associated exact, 95% confidence intervals.

The secondary endpoints of pacing threshold and impedance measurements for the Corox BP LV leads will be summarized at scheduled visits where they were evaluated, using standard measures, including means, standard deviations, medians, minimums, and maximums.

The secondary endpoint for overall incidence of serious adverse events that meet the primary endpoint 1 criteria will be evaluated separately for each Corox BP lead model using the criteria established for primary safety endpoint 1 and 2.

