2.7.2 Missing Data

The reasons for any missing data in the study will be documented. The sponsor will examine both missing-data patterns, which describe which values are observed and which are missing, and the missing-data mechanisms, which concern the relationship between missingness and the values of variables in the study data set [R.J.A. Little and D.B. Rubin, 2002, Statistical Analysis with Missing Data, 2nd edition, Wiley and Sons].

For evaluation of the primary study endpoints (safety endpoints 1 and 2), only patients who achieve 5 years of follow-up or have experienced a serious adverse event prior to 5 years will be included in the evaluation of the associated hypotheses. The secondary endpoint of other SAEs at 5 years, excluded from the primary safety analyses, will be analyzed in similar manner. There will be no imputation for these missing adverse event outcomes.

For purposes of Kaplan-Meier actuarial analyses, described in Section 2.7.1 Trend Analyses, all SAE data on enrolled patients will be included, with follow-up time censored at the time of withdrawal or last completed follow-up visit.

Secondary endpoints, which include successful biventricular pacing, pacing thresholds, sensing and impedance measurements will be analyzed in two ways. Initially, all available results will be summarized by scheduled visit through the 5 years of study follow-up. Afterwards, a last value carried forward (LVCF) will be used to estimate the values at the final 5-year follow-up evaluation.

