- III – Less than ordinary physical activity causes fatigue, palpitation, dyspnea or anginal pain
- IV – Symptoms of cardiac insufficiency or of the anginal syndrome may be present even at rest. If any physical activity is undertaken, discomfort is increased

Observation – an adverse event that does not require additional invasive intervention to resolve

Oversensing – Misinterpretation of cardiac or non-cardiac events as cardiac depolarization, such as T waves, skeletal muscle potentials, and extracardiac electromagnetic interference (EMI)

PG (Pulse Generator) – For this registry, the pulse generator must be either a BIOTRONIK CRT-P or CRT-D

Pneumothorax – Air or fluid in the pleural space surrounding the lung leading to collapse or partial collapse of the lung

Premature Battery Depletion – Reaching Elective Replacement indicator (ERI) before the predicted date

Mechanical Failure – Malfunction of the Corox BP LV lead through a break in the conductor, insulation or connector pin leading to loss of CRT therapy

RV/RA/ICD lead – Right Ventricular/ Right Atrial/ Implantable Cardioverter Defibrillator Lead

Significant Increase in Pacing Threshold – One of the following definitions must be met:

1. An observed increase of 2-fold over the first chronic threshold, provided that the resultant threshold is greater than 5 Volts at 0.5 ms, or
2. An observed threshold higher than the maximum output of the device. Currently, this is 7.5 V at 1.5 ms in the Lumax 340 HF-T and Lumax 540 HF-T CRT-D's.

Chronic threshold is defined as the pacing threshold determined at the patient's 3 month follow-up visit.

Skin Erosion – Deterioration of tissue over an implanted device or the movement of a lead toward or through the skin

Suspected Generator Failure – Pulse generator issue that is potentially an electrical malfunction

CELESTIAL REGISTRY PROTOCOL

Suspected Lead Failure – Corox BP LV Lead issue that is potentially a mechanical or electrical malfunction

Tamponade – Compression of the heart caused by blood accumulation in the space between the myocardium and the pericardium

Threshold Rise – An observed threshold increase of 2-fold over the first chronic threshold, provided that the resultant threshold is greater than 3.5 Volts at 0.5 ms. Chronic threshold is defined as the pacing threshold determined at the patient's 3 month follow-up visit.

Thrombosis – The development of a blood clot in a vein or artery

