#### 3.1 INTENTION-TO-TREAT (ITT) ANALYSIS POPULATION

The intention-to-treat (ITT) population includes all subjects enrolled in the study. The ITT subjects have documentation of informed consented and implant of the Corox LV study lead. This population includes all subjects enrolled in the study.

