### 5.3 SECONDARY ENDPOINTS

There are no formal hypothesis tests associated with the secondary endpoints.

#### 5.3.1 Secondary Endpoint 1

Secondary endpoint 1 examines the successful biventricular pacing in a BIOTRONIK CRT device at scheduled CELESTIAL registry follow-up visits. The mean, standard deviation, minimum, and maximum of the biventricular pacing percentage will be reported for each visit. This endpoint will be evaluated using the subject population defined in section 3.1 Intention-to-Treat (ITT) Analysis Population.

#### 5.3.2 Secondary Endpoint 2

Secondary endpoint 2 examines the rates of serious adverse events excluded from primary safety endpoint. The serious adverse event rates will be reported along with a Kaplan-Meier actuarial graph and case summary will be reported to assess this endpoint. The estimated freedom from adverse event at 5 years along with the standard error and 95% confidence intervals will also be reported. This endpoint will be evaluated using the subject population defined in section 3.1 Intention-to-Treat (ITT) Analysis Population.

#### 5.3.3 Secondary Endpoint 3

Secondary endpoint 3 examines the sensing, pacing threshold, and pacing impedance measurements for the Corox LV leads at scheduled CELESTIAL registry follow-up visits. The mean, standard deviation, median, minimum, and maximum of each measured values be reported for each visit. This endpoint will be evaluated using the subject population defined in section 3.1 Intention-to-Treat (ITT) Analysis Population.

#### 5.3.4 Secondary Endpoint 4

Secondary endpoint 4 examines the individual electrical parameters of the Corox OTW BP LV lead, the Corox OTW-S BP LV lead, and the Corox OTW-L BP LV lead. The electrical parameters presented will be the sensing, pacing threshold, and pacing impedance measurements for each lead model at scheduled CELESTIAL registry follow-up visits. The mean and standard deviation of each measured value will be

reported for each visit. This endpoint will be evaluated using the subject population defined in section 3.1 Intention-to-Treat (ITT) Analysis Population.

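### The mean pacing threshold leaves out leads that no longer capture, and no other planned analysis shows those failures by lead model

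*SAP*

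**What the plan says.** SAP 5.3.3 (secondary endpoint 3, all leads): "The mean, standard deviation, median, minimum, and maximum of each measured values be reported for each visit". SAP 5.3.4 (secondary endpoint 4, by lead model) is narrower: "The mean and standard deviation of each measured value will be" reported at each visit, with no median, range or count of failures. Protocol 2.7 takes the same approach: threshold and impedance "will be summarized at scheduled visits where they were evaluated, using standard measures, including means, standard deviations, medians, minimums, and maximums".

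Both SAP endpoints use the ITT population: "The intention-to-treat (ITT) population includes all subjects enrolled in the study".

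For missing values, Protocol 2.7.2 has two steps: "Initially, all available results will be summarized by scheduled visit through the 5 years of study follow-up", and then "Afterwards, a last value carried forward (LVCF) will be used to estimate the values at the final 5-year follow-up evaluation". The SAP does not carry the second step over.

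Appendix A of the protocol recognizes that a threshold can lie beyond what can be measured. One definition of a significant increase is: "An observed threshold higher than the maximum output of the device". Appendix A also defines an LV lead left connected with LV pacing disabled. Neither document says how such leads enter the threshold summaries.

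**The concern.** A threshold is the lowest output that captures. If nothing captures at maximum output, or LV pacing has been switched off because of threshold or capture, there is no number to enter. A summary of measured values then omits the leads with the worst thresholds, and the omission depends on the outcome being summarized.

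The by-model table is where this matters. Comparing the three Corox models is a stated aim: Protocol 2.6 asks for at least 600 evaluable subjects to evaluate the OTW-L. If one model loses capture more often, its failures leave its mean, and it can look equal to or better than a model that keeps all its leads working.

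**Working it through.** The plan states no figure on this point, so there is none to reproduce. The check has two parts.

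**1. Where would a capture failure be seen?**

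| Planned analysis | Counts capture failures? | Split by model? |
|---|---|---|
| Secondary endpoint 3 (SAP 5.3.3) | Measured values only | No |
| Secondary endpoint 4 (SAP 5.3.4) | Measured values only; mean and SD | Yes |
| Secondary endpoint 2 (SAP 5.3.2) | Yes, if serious: the Table 4 category of high threshold, intermittent capture or no capture | No |
| FDA ad hoc analysis (SAP 2.4, 5.4) | Yes, from 30 days after implant | No |
| Secondary endpoint 1 (SAP 5.3.1) | Indirectly, through pacing percentage | No |
| Secondary endpoints 5 and 6 (SAP 5.3.5, 5.3.6) | No: they use primary endpoint 1 criteria, from which Table 4 removes this category | Yes |

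The poolability tests in SAP section 4 compare models only on the primary endpoints, which have the same exclusion. SAP 5.7 pre-specifies no further subgroup analyses. SAP 5.3.4 is therefore the only planned by-model evidence on threshold, or on failures in the Table 4 capture category.

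Neither existing provision repairs this. ITT sets who is eligible for the table, but a subject without a value adds nothing to a mean. Last value carried forward would usually supply a reading from before the failure.

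**2. How far could the mean move?**

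Inputs:
- Observed mean 1.2 and SD 1.1, from Protocol Table 2 (everesT, 3 months, 99 tests, 0.5 ms), read as volts.
- Value assigned to a failed lead: 7.5 V, the maximum output in Appendix A, quoted there at 1.5 ms for two CRT-D models.
- Share f of leads with no measurable threshold: not given. Assumed range 0.5% to 5.6%. Table 4 gives 3.6% to 5.6% for the pooled category.

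Formulas:
- Mean of all leads = (1 − f) × 1.2 + f × 7.5
- Variance of all leads = (1 − f) × (1.1² + 1.2²) + f × 7.5² − (mean of all leads)²
- Median of all leads = the 0.5/(1 − f) quantile of the measured values

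| f | Mean (V) | Change | SD | Median falls at measured percentile |
|---|---|---|---|---|
| 0.5% | 0.995 × 1.2 + 0.005 × 7.5 = 1.23 | +2.6% | 1.18 | 50.3 |
| 1% | 1.26 | +5.2% | 1.26 | 50.5 |
| 2% | 1.33 | +10.5% | 1.40 | 51.0 |
| 3.6% | 1.43 | +18.9% | 1.59 | 51.9 |
| 5.6% | 0.944 × 1.2 + 0.056 × 7.5 = 1.55 | +29.4% | 1.80 | 53.0 |

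The mean and SD are sensitive to f; the median hardly moves. SAP 5.3.3 has a median and SAP 5.3.4 does not.

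*Reversal between models (hypothetical).* Model A has no failures and a mean of 1.3 V. Model B has a measured mean of 1.2 V and 5% non-capture. SAP 5.3.4 would show B lower. With failures at 7.5 V, B's mean is 0.95 × 1.2 + 0.05 × 7.5 = 1.515 V, above A. The order reverses once B's non-capture exceeds (1.3 − 1.2)/(7.5 − 1.2) = 1.6%.

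**The case against.** The strongest reply is that the registry does not lose capture failures. Secondary endpoint 2 reports their rate, a Kaplan-Meier curve, 5-year freedom from event and case summaries in all enrolled subjects. The FDA ad hoc analysis adds no-capture events from 30 days, and elevated thresholds at routine visits even when they are not protocol adverse events. This stands for the pooled result. Secondary endpoint 2 counts serious events, which Protocol 2.2 links to invasive intervention for the primary endpoint, so a lead managed by disabling pacing might be missed there. But that lead meets both adverse-event conditions in Protocol 7.6, and the ad hoc analysis does not require an intervention. A reader might infer that the registry as a whole will overstate chronic performance; the documents do not support that.

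The reply does not reach the by-model comparison. Case summaries might name the model, but no by-model tabulation is planned. A loss of capture classified as a late dislodgement or a suspected lead failure could reach endpoints 5 and 6. The Table 4 capture category cannot.

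A reader might also extend the point to impedance. That fails: an impedance reading does not need capture, and Appendix A defines impedance failure by numeric limits, so failing readings enter the summary.

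The fall in Table 2 from 99 tests to 15 between 3 and 6 months, with lower means and maxima, might be read as failing leads dropping out. It comes from another study, no cause is stated, and a maximum over 15 tests is expected to be lower than one over 99.

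Two further cautions stand. How the case report form records non-capture is not stated, so dropping out is inferred from the wording on measured values. Protocol 3.2.4 also bars enrollment without effective CRT, which screens out early failures.

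**Conclusion.** The point holds for pacing threshold. The plan has no rule for a lead without a measurable threshold, and leaving such leads out biases the mean low. Its practical weight lies in SAP 5.3.4, where mean and SD stand alone and no other planned by-model analysis counts failures in the capture category.

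The size cannot be found from the documents. The range of about +3% to +29% is an illustration. Its top is an upper end, because Table 4's 5.6% includes high but measurable thresholds that stay in the mean, and it is an event rate from prior studies, not a prevalence at a visit. The 7.5 V value is a convention: the ceiling is quoted at 1.5 ms and Table 2 is at 0.5 ms, and a lead switched off for a high threshold may lie below it.

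These are descriptive secondary endpoints with no hypothesis tests, and no primary conclusion depends on them. Severity is modest, but the change is worth making because it can alter which model looks better.

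**What to change.** In SAP 5.3.4, and in 5.3.3 for all leads, add for each visit:

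1. The number of leads at risk, the number with a threshold, and the number not measurable by reason: no capture at maximum output, LV pacing off or lead abandoned for threshold or capture reasons, explanted or replaced, visit missed.
2. The proportion with a threshold above 3.5 V at 0.5 ms (the follow-up limit for Elevated Threshold in Appendix A) or no capture, with an exact 95% CI. Count leads off or abandoned for threshold or capture reasons as failures. State how readings at other pulse widths are classified, since Protocol 3.2.5 does not fix the pulse width.
3. The median and other quantiles, with non-capture ranked above the highest measured value.

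Separately, report the proportion of impedances out of range (≤ 200 or ≥ 2000 Ohms). The reason is different: low and high failures can offset each other in a mean. Also state in the SAP whether the protocol's last-value-carried-forward step is kept.

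A paired change from the first chronic threshold need not be required. Appendix A ties that reading to the 3-month visit, and with enrollment up to 180 days after implant and 6-monthly CRT-P visits, many patients may not have one.

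The cost is a few table rows, largely from data already collected, though the reason for an unmeasurable threshold must be recoverable from the case report or adverse event forms. Reported thresholds may look slightly less favourable.

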For the sample size calculation, a maximum loss to follow-up of 10% per year (50% over 5 years) was assumed. The loss to follow-up rate encompasses all causes for subjects to be exited from the study, including subject death, device explants, patient directed withdrawals, physician directed withdrawals, and loss of contact with the subject. BIOTRONIK will make every effort to limit the loss to follow-up, for reasons other than subject death and device explants unrelated to device design or performance, to less than 20% of the total registry enrollment cohort.

Minimum cohort size

The pre-specified secondary analysis will be conducted as an ad hoc analysis, meaning no testable hypothesis is being stated. Therefore, the minimal cohort size to analyze each lead model is based on an assumption of an equal 1/3 distribution of each lead model being enrolled in the CELESTIAL Registry. For the evaluation of the Corox OTW-L BP lead, a minimum of 600 evaluable subjects will be necessary.

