### 3. ANALYSIS POPULATIONS

The primary and secondary endpoints analyses will be conducted based on pre-defined populations as described below.

The primary endpoint per-protocol analysis population will be used to conduct the primary endpoints 1 and 2 analyses because these endpoints are based on SAEFR and SAE rates at 5 years post-implant respectively. The secondary endpoint per-protocol analysis population will be used to conduct the secondary endpoints 5 and 6 analyses because these endpoints examine primary endpoints 1 and 2 based on originally implanted lead models; therefore, are examined at 5 years post-implant. The intention-to-treat population will be used to conduct the secondary endpoints 1 through 4 analyses and all additional data of interest because these endpoints are continuous and examine measurements and event rates throughout the study; therefore, are not limited to only examining subjects who complete 5 year follow-up.

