## **5.6 ADHERENCE AND RETENTION ANALYSIS**

A 50% loss to follow-up over 5 years (10% per year) will be assumed.

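### The SAP describes pacing threshold, sensing and impedance by raw visit summaries on whoever remains, so an apparent 5-year trend cannot be separated from a change in who is measured

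*SAP*

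**What the plan says.** SAP 5.3.3 (secondary endpoint 3) plans, for sensing, threshold and impedance: "The mean, standard deviation, median, minimum, and maximum of each measured values be reported for each visit". SAP 5.3.4 (secondary endpoint 4) repeats this by lead model with mean and SD only. Protocol 2.7 likewise summarises threshold and impedance at scheduled visits "using standard measures, including means, standard deviations, medians, minimums, and maximums".

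Both endpoints use the ITT set. SAP section 3 explains that these analyses "are not limited to only examining subjects who complete 5 year follow-up", so the contributors differ from visit to visit.

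On attrition, SAP 5.6 states: "A 50% loss to follow-up over 5 years (10% per year) will be assumed". Protocol 2.6 calls it an upper limit: "a maximum loss to follow-up of 10% per year (50% over 5 years) was assumed". It also defines the loss broadly: "The loss to follow-up rate encompasses all causes for subjects to be exited from the study, including subject death, device explants", along with withdrawals and loss of contact.

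Protocol 2.7.2 plans two analyses of the electrical parameters. In the first, "all available results will be summarized by scheduled visit through the 5 years of study follow-up". The second carries the last value forward to the 5-year evaluation. The same section promises to examine missing-data patterns and mechanisms. The SAP mentions neither LVCF nor that examination.

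Appendix A of the protocol defines Threshold Rise by comparing a lead with itself: "An observed threshold increase of 2-fold over the first chronic threshold", subject to a minimum resulting voltage. No analysis section uses the term.

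**The concern.** The registry sets out to evaluate acute and chronic LV lead parameters through 5 years. A reader will get that by looking down a column of visit means. If the patients who leave had higher or lower thresholds than those who stay, the column moves although no lead has changed, or stays flat while leads drift. Death and explant count as exits, so it is plausible that leaving is related to the condition of the heart or the lead.

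Three features add to this:

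- Protocol 4.1 has CRT-D patients seen every 3–4 months and CRT-P patients every 6, so the device mix can differ between visits.
- Enrolment falls 7–180 days after implant, so first readings are taken at different lead ages.
- The comparison of lead models in endpoint 4 is affected if exit differs by model.

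Each lead has repeated readings, so the data to separate the two explanations will exist. The plan does not use them that way.

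**Working it through.** **1. The plan's attrition figures.** Enrolled = evaluable / (1 − loss): 240/0.5 = 480 and 1000/0.5 = 2000, as stated in Protocol 2.6 and SAP 1.1. For 2500 enrolled, 50% loss leaves 1250 at 5 years. Compounding 10% per year leaves 2500 × 0.9⁵ = 2500 × 0.5905 = 1476, a 41% loss.

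**2. Effect of exit when no lead changes.** Shift in the visit mean = −(share lost) × (leaver mean − stayer mean). The SDs are the 3-month values in Protocol Table 2 (1.1 V, 202 ohms). The gap between leavers and stayers is not in the documents; I assume 0.1 to 0.5 SD.

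| Loss | Threshold shift | Impedance shift |
|---|---|---|
| 50% | 0.5 × (0.1 to 0.5) × 1.1 = 0.06 to 0.28 V | 0.5 × (0.1 to 0.5) × 202 = 10 to 51 ohms |
| 41% | 0.05 to 0.23 V | 8 to 41 ohms |

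The standard error of the 5-year mean is 1.1/√1250 = 0.031 V and 202/√1250 = 5.7 ohms, so most of these shifts would look like a precisely estimated trend.

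**3. The same by simulation.** Assumptions: lognormal threshold with mean 1.3 V and SD 1.2 V (Table 2, one month); log-scale correlation between readings 0.7–0.8 (0.63–0.75 in volts); 50% exit; odds of leaving 1.25–1.5 per SD of the log first reading. With no lead changing, the visit mean falls about 0.07–0.16 V. With an odds ratio of 1 there is no shift. A plain paired change in those who stay errs the other way, by 0.02–0.06 V.

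**4. What Table 2 can show.** The everesT mean threshold is 1.2 V on 99 tests at 3 months and 0.8 V on 15 tests at 6 months. Suppose the 15 are among the 99 and no lead changed. The other 84 then need a 3-month mean of (99 × 1.2 − 15 × 0.8)/84 = 106.8/84 = 1.27 V, which is unremarkable. Who was measured could account for the whole fall; so could a real change. The raw means do not tell them apart.

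**5. What LVCF would do.** With linear drift and exits spread evenly, a leaver's last value holds half the 5-year drift on average. Share recovered = (1 − loss) + loss/2. At 50% loss that is 0.75; at 41% it is 0.80. A true rise of 0.15 V would appear as about 0.11 V.

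**6. Precision.** The year-5 patients are a subset of those at the start, so the two means are correlated. With SD 1.2 V, the SE of their difference is 1.2 × √(1/2500 + 1/1250 − 2ρ/2500) = 0.032 V at ρ = 0.63 and 0.029 V at ρ = 0.75. For paired change it is 1.2 × √(2(1 − ρ)/1250) = 0.029 and 0.024 V. The gain is about 8–18%.

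**The case against.** The strongest reply is that Protocol 2.7.2 already provides for this. LVCF keeps leavers in the 5-year estimate. In the scenario of step 3, with exits spread over yearly visits, it moves by less than 0.01 V when no lead changes. That stands, and it would be wrong to say that raw visit means are all the documents plan. But LVCF freezes leavers' values, covers only the final time point, and is missing from the SAP.

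Second, within-lead deterioration is not ignored. High pacing threshold is defined against the previous measured value and is reported under secondary endpoint 2. The FDA-requested analysis counts every subject with an elevated threshold at a routine visit from day 30, by Kaplan–Meier. This stands for threshold as an event. Sensing and impedance have no comparable analysis outside adverse events.

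Third, these endpoints carry no hypotheses, and 0.07–0.16 V is about 2–5% of the 3.5 V follow-up cut-off in Appendix A. That limits the weight of the point. It does not remove it, because description is the whole purpose of these endpoints.

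Three stronger readings should be resisted:

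- A reader might infer that the cohort is planned to halve. Fifty percent is a maximum assumed for sizing.
- A reader might take Table 2 as a demonstration of selective loss. It comes from another study, and the protocol does not say why only 15 were tested at 6 months.
- A reader might treat the two visit means as independent (SE 0.042 V) and claim a 30–42% precision gain from pairing. The samples are nested, and step 6 gives 8–18%.

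**Conclusion.** The point holds in a limited form. As the SAP stands, a trend in mean threshold, sensing or impedance cannot be separated from a change in who is measured, and no within-lead analysis of the continuous readings is planned. The SAP has also dropped the two elements of Protocol 2.7.2 that bear on this.

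The argument rests on possible bias, with precision a minor benefit. Neither the size nor the direction of that bias follows from the documents, which do not relate exit to threshold. The 0.07–0.16 V figure depends on assumed odds ratios and on 50% exit; if exit is unrelated to the readings, there is no bias. The primary endpoints and their conclusions are not touched. This is a cheap improvement to a descriptive analysis.

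**What to change.** Keep the raw visit summaries and state the number of leads contributing at each visit.

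In SAP 5.3.3 and 5.3.4, add a mixed model for repeated measures on all visits, with threshold on the log scale. Measure time from implant, because first readings fall at different lead ages. Report within-lead change from the first routine follow-up reading by year, overall and by lead model, with 95% confidence intervals. The first routine reading is suggested as reference because patients enrolled late in the 7–180 day window may lack the 3-month value that Appendix A uses. A model on all readings is preferable to plain paired differences, which carry the smaller bias in step 3.

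Reconcile the SAP with Protocol 2.7.2: use this model in place of LVCF or beside it, and say where missing-data patterns and mechanisms will be examined.

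The cost is SAP wording and one model per parameter, with no new data. The downside is a missing-at-random assumption, which extends to exits by death or explant and should be stated beside the raw summaries.
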